9.1.3 Missing data for daily worst endometriosis-related pain question

If the subject do not complete the daily diary, then the day after the subject will be asked question 14 in the e-Diary. If the answer to question 14 is "I was in too much pain from endometriosis", the missing data for the previous day will be assigned a NRS of 10 for worst endometriosis-related pain (taking a worst-case approach). Otherwise, the daily score remains to be missing.

9.1.4 The mean daily NRS score

The baseline value for the mean daily NRS scores is defined as the average of the mean daily NRS scores of the two run-in cycles (cycles -2 and -1). For all post baseline cycles (cycles 1 to 10) the change in the mean daily NRS scores from baseline will be calculated using this definition of the baseline value.

9.1.4.1 The mean daily NRS score for worst endometriosis related pain

For each cycle, at least 50% of the NRS scores are required to be observed (including the imputed values as described in subsection 9.1.3) for both the menstrual period and the non-menstrual period (as defined in subsection 9.1.2) to be allowed to calculate the mean daily NRS score for that particular cycle. So if above 50% of the daily NRS scores are missing in either period of that cycle, the mean daily NRS score for worst endometriosis related pain for that cycle should be missing.

As missing daily NRS scores may not be appropriately balanced across menstrual period and non-menstrual period, the mean daily NRS score will be weighted by the lengths of the menstrual period and non-menstrual period to adjust for this potential imbalance.

So the mean daily NRS score is calculated as

$$\frac{l_{mp}\overline{x}_{mp} + l_{non-mp}\overline{x}_{non-mp}}{l_{mp} + l_{non-mp}}$$

Where l_{mp} is the number of days in the menstrual period of the cycle (as defined in subsection 9.1.2), l_{non-mp} is the number of days in the non-menstrual period of the cycle in question (as defined in subsection 9.1.2), \bar{x}_{mp} is the mean daily NRS score based on the observed daily NRS scores (question 1) during the menstrual period (including imputations as described in 9.1.3), and \bar{x}_{non-mp} is the mean daily NRS score (question 1) based on the observed daily NRS scores during the non-menstrual period (including imputations as described in 9.1.3).

If the subject does not have a menstrual period in a cycle the mean daily score is calculated as a simple mean, however if more than 50% of the daily NRS scores are missing the mean daily NRS will be considered missing

9.1.4.2 The mean daily NRS score for worst dysmenorrhea

For each cycle the mean daily NRS score for worst dysmenorrhea is defined as the mean daily NRS score for worst endometriosis related pain (question 1) during the menstrual period of that cycle (as defined in subsection 9.1.2).

If above 50% of the daily NRS scores in the menstrual period of a cycle are missing, the mean daily NRS score for worst dysmenorrhea for that cycle should be missing.

9.1.4.3 The mean daily NRS score for worst non-menstrual pelvic pain

For each cycle the mean daily NRS score for worst non-menstrual pelvic pain is defined as the mean daily NRS score for worst endometriosis related pain (question 1) during the non-menstrual period of that cycle (as defined in subsection 9.1.2).

If above 50% of the daily NRS scores in the non-menstrual period of a cycle are missing, the mean daily NRS score for worst non-menstrual pelvic pain for that cycle should be missing.

9.1.4.4 The mean daily NRS score for worst impact of endometriosis related pain on the subject ability to function

The mean daily NRS score for worst impact of endometriosis related pain on the subject ability to function will be based on the mean of question 5 to 8. The mean daily NRS score will be calculated if the mean daily NRS score for worst endometriosis related pain is calculated, it will be calculated using the same weighting scheme as used in section 9.1.4.1.

9.1.5 Analgesics use

Analgesic use will be used both as an endpoint by itself and as an adjustment variable for other endpoints. The baseline value for different measures of analgesics use is defined as the average of that measure in cycles -2 and -1.

9.1.5.1 Percentage of days with analgesics use

The percentage of days with analgesics use will be calculated for each cycle and separately for mild analgesics, strong analgesics and any analgesics. If the mean daily NRS score for worst endometriosis related pain is not calculated for a specific cycle due to many missing daily e-Diaries, then the three percentage of days with analgesics should not be calculated either.

The percentage of days with mild analgesics use is based on the first part of question 13. The percentage of days with strong analgesics use is based on the second part of question 13. The percentage of days with any analgesics use is based on both the first and the second part of question 13.

For adjustment of the secondary endpoints worst dysmenorrhea and worst non-menstrual pelvic pain similar variables will be needed for mild and strong analgesics just only using data from the e-Diary from the menstrual period and non-menstrual period of the cycle, respectively. If the mean daily NRS for worst dysmenorrhea or worst non-menstrual pelvic pain is not calculated due to to many missing variables the corresponding percentage of days with mild analgesics should not be calculated either.

9.1.5.2 Total and average doses of analgesics

For each cycle the total dose of mild analgesics is calculated by summing the daily doses from the first part of question 13 (if the answer is no, then the dose is 0 mg). For each cycle the total dose of strong analgesics is calculated by summing the daily doses from the second part of question 13 (if the answer is no, then the dose is 0 mg). The average doses are calculated as the total dose divided by the number of times question 13 has been answered during that cycle.

The total and average doses will be calculated if the mean daily NRS score for worst endometriosis related pain is calculated, it will be calculated using the weighting scheme as described in section 9.1.4.1.

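### SAP 9.1.5.2 is internally inconsistent on how total and average rescue-analgesic dose are derived, and its plain-sum total falls as diary completion falls

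*SAP*

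**What the plan says.** Total and average doses of mild and strong rescue analgesics are a secondary endpoint (SAP 2.5). SAP 9.1.5.2 derives them in two paragraphs.

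The first is unweighted: "For each cycle the total dose of mild analgesics is calculated by summing the daily doses from the first part of question 13", with the note that "if the answer is no, then the dose is 0 mg". Strong analgesics are handled in the same way from the second part of the question. For averages: "The average doses are calculated as the total dose divided by the number of times question 13 has been answered during that cycle".

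The second paragraph says the doses are computed when the cycle's mean daily pain score is computable, and then that "it will be calculated using the weighting scheme as described in section 9.1.4.1".

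Section 9.1.4.1 gives that scheme as `(l_mp*x_mp + l_non*x_non)/(l_mp + l_non)`. Each `l` is a number of days and each `x` is a mean; the menstrual term, for instance, "is the mean daily NRS score based on the observed daily NRS scores (question 1) during the menstrual period". A cycle counts if, in both the menstrual and the non-menstrual period, "at least 50% of the NRS scores are required to be observed (including the imputed values as described in subsection 9.1.3"). The imputation covers days missed because of too much pain: "the missing data for the previous day will be assigned a NRS of 10 for worst endometriosis-related pain".

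**The concern.** The two paragraphs do not describe the same quantity. A sum of recorded doses is an amount per cycle. The 9.1.4.1 formula returns an amount per day. No precedence is given, and no version of the formula is adapted to a total. Two programmers working from this text could produce different tables for the same endpoint.

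The plain sum is also not a safe default. Zero is assigned only to a negative answer, so an unanswered day contributes nothing and has the same effect as a day without use. Up to half the days in each period may be unanswered. Days imputed as a pain score of 10 count toward the 50% but carry no dose, and Protocol 10.3 rules out entering one later.

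This matters because change from baseline is tabulated by treatment (SAP 9.3.1). Baseline comes from run-in cycles in which inclusion criterion 13 requires at least 80% diary completion on average, whereas a treatment cycle is accepted down to 50% per period. Cycles with more than 20% missing diary days are removed only from the per-protocol set (SAP section 5), and this endpoint is summarised only in the ITT set (SAP 9.3).

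**Working it through.** There is no figure in the plan to reproduce, so the check applies both rules to one example cycle.

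**Assumed inputs, not from the documents:** a 28-day cycle; 5 menstrual days at 800 mg and 23 other days at 200 mg; use on missed days equal to use on observed days of the same period; question 13 counted as answered on every completed diary day. Completion patterns were kept within the 50% rule of SAP 9.1.4.1.

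**Formulas**

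- Plain sum: `n_mp*800 + n_non*200`, where `n` is the number of completed days in the period.
- First-paragraph average: plain sum / `(n_mp + n_non)`.
- 9.1.4.1 quotient: `(5*800 + 23*200)/28 = 8600/28 = 307.1` mg per day, whatever the completion pattern.
- 9.1.4.1 numerator alone: `5*800 + 23*200 = 8600` mg per cycle, also constant.

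| Menstrual days completed | Other days completed | Completion | Plain sum (mg) | First-paragraph average (mg/day) |
|---|---|---|---|---|
| 5/5 | 23/23 | 100% | 8600 | 307.1 |
| 4/5 | 19/23 | 23/28 = 82.1% | 3200 + 3800 = 7000 | 7000/23 = 304.3 |
| 4/5 | 16/23 | 20/28 = 71.4% | 3200 + 3200 = 6400 | 6400/20 = 320.0 |
| 3/5 | 12/23 | 15/28 = 53.6% | 2400 + 2400 = 4800 | 4800/15 = 320.0 |
| 3/5 | 23/23 | 26/28 = 92.9% | 2400 + 4600 = 7000 | 7000/26 = 269.2 |
| 5/5 | 12/23 | 17/28 = 60.7% | 4000 + 2400 = 6400 | 6400/17 = 376.5 |

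**Total.** True use is 8600 mg in every row. The plain sum is 18.6% low at 82% completion, 25.6% low at 71% and 44.2% low at 54%.

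**Change from baseline with unchanged use.** Take baseline at 82% completion (7000 mg). At 71%, `6400/7000 - 1 = -8.6%`. At 54%, `4800/7000 - 1 = -31.4%`. The second case lies close to the limit the SAP accepts and is not a forecast of completion.

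**Average.** With a complete diary, or equal completion proportions in the two periods, both rules give 307.1. With near-balanced completion (second row) they differ by 0.9%. In the two most unbalanced patterns, the first-paragraph average is 269.2 (-12.3%) and 376.5 (+22.6%), against 307.1 weighted.

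**The case against.** The strongest reply is grammatical. In the second paragraph the subject, doses, is plural and *it* is singular. The nearest singular noun is the mean daily pain score, which is what 9.1.4.1 derives. On that reading the clause merely describes the variable used for gating, and the first paragraph is the only dose rule. This cannot be excluded, so the text does not strictly prove two competing rules. It is the weaker reading, however. SAP 9.1.4.4 uses nearly the same construction for the pain-impact score ("it will be calculated using the same weighting scheme as used in section 9.1.4.1"), where it plainly refers to the variable being derived, and restating how the pain score is weighted would serve no purpose in a dose section. Even if the reply is accepted, the plain sum keeps its dependence on completion.

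A second reply is that the weighting can be read coherently, with the numerator as the total and the quotient as the average. That is sensible, but the SAP does not say it, and it contradicts the first paragraph whenever days with a dose are missing.

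Third, the protocol planned negative-binomial regression for this endpoint (Table 9-2) and describes an offset for counts relative to cycle days (9.6.3), which makes a raw sum a natural starting point. The SAP no longer fits that model, so no offset corrects the sum.

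Fourth, diary completion is supported by reminders and site review (Protocol 6.1 and 10.3), so severe loss may be uncommon. This limits the likely size but does not remove the defect.

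**Conclusion.** The point holds as a minor one. SAP 9.1.5.2 needs a single stated derivation. Whichever way *it* is read, something is wrong: either the weighting conflicts with the first paragraph and is undefined for a total, or a plain sum remains that partly measures diary completion. The sizes above (-8.6%, about -31% near the limit, and 269 to 376 mg against 307 mg) depend on the assumed doses and completion patterns, so they illustrate rather than estimate.

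Three stronger readings are not supported:

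- A reader might set 307 mg against 8600 mg as the size of the error. The first is per day and the second per cycle. The contrast shows only that the printed formula cannot be a total.
- A reader might infer that question 13 appears only after a yes to question 12, which would make the first-paragraph average a dose per day of use. The SAP prints no such condition, and its percentage-of-days measure (9.1.5.1) is built on the same question. The complete diary is in Protocol Appendix 1, which is not in the text available here. No figure should rest on this.
- A reader might extend the problem to the main results. The primary endpoint does not use dose, and the responder rule (SAP 9.1.6) uses percentage of days with analgesics. The SAP plans no inferential analysis, so only descriptive summaries of one secondary endpoint are affected.

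**What to change.** Replace both paragraphs of SAP 9.1.5.2 with one derivation for each analgesic type:

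- Total dose per cycle = `l_mp*d_mp + l_non*d_non`.
- Average daily dose = total / `(l_mp + l_non)`.
- `d` is the mean daily dose over completed diary days in that period, counting 0 mg when question 12, or the relevant part of question 13, is answered no.
- For a cycle without menses, total = cycle length x simple mean daily dose over completed diary days.
- Keep the existing rule that ties calculability to the pain score, but set the dose to missing if a period has no completed diary day. This can arise because imputed pain days count as observed.
- Drop the division by the number of question 13 answers.

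State the assumption openly: use on missed days is taken to equal use on observed days of the same period. This may understate use on days missed because of too much pain.

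Simply deleting the weighting clause would also end the ambiguity, but would leave a total that moves with diary completion. The cost is a revision of the derivation text and a small programming change, with no new data.

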9.1.6 Responder status

Twelve different definitions of responder status are being used in this trial, one for each combination of the 4 mean daily NRS score defined in section 9.1.4 and the 3 thresholds \geq 30%, \geq 50% and \geq 70%.

A subject is defined as being a responder in a specific cycle if the mean daily NRS score is reduced with at least the threshold value compared to baseline and that the percentage of days on any analgesics has not increased by more than 10% since baseline.

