#### 6.1 Activities between Clinic Visits

In this trial, a menstrual cycle is considered the period between day 7 of return of menses (RM+7) in a cycle until the following RM+7. Visits on RM+7 can be scheduled on RM+6-10, i.e. day 6 to day 10 of return of menses. Similarly, visits on LH+7 can be scheduled on LH+6-9, i.e. 6-9 days after LH surge, which is either assessed by the subject using LH surge kits at home or estimated by the site staff based on subject's cycle length. If subjects do not have menstrual bleeding in a cycle during the treatment and follow-up period, the RM+7 visit in that cycle must be arranged within 35 days of the last RM+7 visit.

The review of the e-Diary, which covers compliance with e-Diary completion and analgesic use should be performed by site staff regularly between clinic visits.

Contraception counselling and condoms will be offered to subjects as needed throughout the trial.

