# 7.2.1.5 Analgesic Use

Rescue analgesics for endometriosis-related pain will be limited to ibuprofen and/or hydrocodoneacetaminophen in this trial. As a mild analgesic, ibuprofen will be provided in the form of 200 mg oral tablets to subjects for their use on an as-needed basis. The specific dosing regimen of ibuprofen will be advised by the investigator but the maximum amount is 800 mg (4 tablets) per dose and 3200 mg (16 tablets) per day in accordance with the label of prescription ibuprofen doses. Subjects will be instructed not to use other analgesics unless necessary. If there is a need to change analgesics, subjects should discuss with investigators, who may prescribe a strong rescue analgesic hydrocodone-acetaminophen at a dose of 5 mg hydrocodone plus 300 mg or 325 mg acetaminophen. Only oral tablet formulation of combined hydrocodone-acetaminophen (i.e. hydrocodone bitartrate/acetaminophen) is allowed in the present trial. The specific dosing regimen of hydrocodone-acetaminophen is decided by the investigator based on subjects' needs and tolerability in accordance with the labelling of the product.

After subjects' entry into the run-in period, investigators can either advise ibuprofen dosing regimen or prescribe hydrocodone-acetaminophen by taking subjects' preference and history of analgesic use into consideration. Investigators should not take the initiative to suggest any modifications to the subject's current rescue analgesic regimen.

Subjects will be asked to follow the investigators' instructions on the type(s) and dose(s) of rescue analgesics they can use and whether they can take different rescue analgesics at the same time. Use of any other analgesics for endometriosis-related pain is prohibited from the start of run-in to the end-of-trial (see section 4.3.1 for prohibited analgesics). Any prophylactic use of analgesics is also prohibited from the start of run-in to the end-of-trial.

In order for sites to perform drug accountability, subjects will be instructed to bring back any packages of used and unused ibuprofen to the site at each visit.

The type and amount of mild and/or strong rescue analgesics used will be reported by subjects using the e-Diary. If subjects indicate any use of other analgesics for endometriosis-related pain, the specific name and dose of the analgesics will be noted in the e-CRF, while subjects will report the number of tablets taken in the e-Dairy.

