## 7.4.17 Concomitant Medication

The use of any concomitant medication within the last 3 months prior to informed consent for participation in the trial and throughout the trial will be recorded. Recording of concomitant medication other than ibuprofen and hydrocodone-acetaminophen will be performed at all visits. Any changes in concomitant medications or treatments must be recorded at each visit. Investigators' instructions for ibuprofen dosing and prescriptions of hydrocodone-acetaminophen will be recorded in the e-CRF.

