9. Did you ha □ No □ Yes	ave vaş	ginal ble	eding i	n the pa	ıst 24 ho	ours?				

If the subject had vaginal bleeding in the past 24 hours:

10. Please describe your bleeding in the past 24 hours.
□ Spotting (tiny amount of blood on underwear or panty liners)
□ Light (requiring 1-3 sanitary pads or tampons per day)

□ Moderate (requiring 4-6 sanitary pads or tampons per day)
 □ Heavy (requiring more than 6 sanitary pads or tampons per day)

- 11. Was your bleeding related to your period (i.e., menstrual bleeding)?
 - □ No
 - \Box Yes

12. Have you taken any medication to reduce your endometriosis-related pain in the past 24 hours?

🗆 No

□ Yes

13. Which medication did you take for your endometriosis-related pain in the past 24 hours? Please answer "No" or "Yes" for each medication listed below.

MOTRIN 200 mg

□ No

□ Yes

Hydrocodone-acetaminophen (prescribed)

🗆 No

□ Yes

Other \Box No

 \square Yes

The subjects will be asked to specify the number of tablets taken for each medication where "yes" is selected: "Please specify the number of tablets you took."

<An arrow spin will be available to list the number of tablets for each medication where "yes" is ticked.>

If the subject did not answer the diary yesterday:

14. Please let us know why you did not complete the diary yesterday.

- \Box I was in too much pain from endometriosis
- \Box I forgot

 \Box Other reason

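### The responder condition on any analgesics ignores recorded use of other analgesics, so two subjects with the same analgesic days can get opposite responder status

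*SAP*

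**What the plan says.** SAP 9.1.6 sets up twelve responder definitions: four NRS-based scores, each with thresholds of 30%, 50% and 70%. Every one also requires that "the percentage of days on any analgesics has not increased by more than 10% since baseline".

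The analgesic variable comes from SAP 9.1.5.1: "The percentage of days with any analgesics use is based on both the first and the second part of question 13". The first part is ibuprofen (MOTRIN 200 mg) and the second is prescribed hydrocodone-acetaminophen. For baseline, SAP 9.1.5 states: "The baseline value for different measures of analgesics use is defined as the average of that measure in cycles -2 and -1".

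The diary in SAP 9.1 collects more than this. Question 12 opens with "Have you taken any medication to reduce your" and goes on to name endometriosis-related pain. Question 13 then asks about three items, the third being Other, with a tablet count for each item answered yes.

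Protocol 7.2.1.5 prohibits such use ("Use of any other analgesics for endometriosis-related pain is prohibited from the start of run-in to the end-of-trial") but still provides for capturing it: "If subjects indicate any use of other analgesics for endometriosis-related pain, the specific name and dose of the analgesics will be noted" in the e-CRF.

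Under SAP 5, more than one day of prohibited analgesics in a cycle is a major deviation that removes that cycle from the per-protocol analysis. SAP 9.3 summarises every endpoint except the primary in ITT only.

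**The concern.** The purpose of an analgesic condition in a responder definition is to avoid crediting a fall in pain score that came with more analgesic use. Under the SAP derivation, a day treated only with an Other analgesic counts as a day without analgesics. A subject who adds such days on treatment can keep responder status that an equal number of ibuprofen days would have cost her.

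The omission also enters the baseline. A subject with Other-only days in run-in has her baseline use understated, so a later move to the permitted rescue products looks like an increase and can cost her responder status.

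The condition feeds all twelve definitions of one secondary endpoint. That endpoint is still reported: it is in SAP Table 9-1 and is not among the items dropped in SAP 12.

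The same sentence has a second gap. It does not say whether the 10% is a relative change or a difference in percentage points.

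**Working it through.** The documents give no figure to reproduce here, so the check applies the stated rule to constructed subjects who are taken to meet the NRS threshold.

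**Inputs**
- Analgesic measure under the SAP: days with part 1 or part 2 of question 13 answered yes, divided by cycle days (SAP 9.1.5.1).
- Full measure for comparison: days with any of the three parts answered yes.
- Baseline: average over cycles -2 and -1 (SAP 9.1.5).
- Cycle length: 28 days assumed, diaries complete. The range 24 to 35 days is taken from inclusion criterion 11 (Protocol 4.1.1). That criterion governs run-in cycles, so the range is illustrative for treatment cycles.
- Two readings of the limit. Points: pass if current % − baseline % ≤ 10. Relative: pass if current % ÷ baseline % ≤ 1.10.

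**Case 1: same analgesic days, opposite status.** Both subjects have a baseline of 10/28 = 35.7%, all permitted rescue.
- 14 ibuprofen days: 14/28 = 50.0%, which is +14.3 points and +40% (14/10). Fails on both readings.
- 14 Other-only days: the SAP measure is 0/28 = 0%. Passes on both readings.

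**Case 2: modest wrong pass.** Baseline 10/28 = 35.7%; on treatment, 10 rescue days plus 3 Other-only days.
- SAP measure: 10/28 = 35.7%, no change. Passes.
- Full measure: 13/28 = 46.4%, which is +10.7 points and +30% (13/10). Fails on both readings.

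**Case 3: wrong fail.** Each run-in cycle has 7 rescue days plus 3 Other-only days; on treatment, 10 rescue days.
- SAP measure: 7/28 = 25.0% to 10/28 = 35.7%, which is +10.7 points and +42.9% (10/7). Fails on both readings.
- Full measure: 10/28 to 10/28, no change. Passes.

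**Smallest number of days that matters.** Let rescue use stay at *b* days (at least 1), with *o* Other-only days in a cycle of *L* days. A wrong pass on both readings needs *o*/*L* > 0.10 and *o*/*b* > 0.10, that is *o* > 0.1*L* and *o* > 0.1*b*. Since *b* < *L*, the first inequality binds.
- *L* = 24 to 29: 0.1*L* runs from 2.4 to 2.9, so *o* = 3.
- *L* = 30 to 35: 0.1*L* runs from 3.0 to 3.5, so *o* = 4. At *L* = 30, 3 days is exactly 10% and still passes.

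**The two readings of 10%.** This gap needs no Other use. Going from 10 to 12 ibuprofen days in 28 is 2/28 = +7.1 points, which passes, and 12/10 = +20%, which fails. At zero baseline use a relative change cannot be computed. Rewriting the limit as current ≤ 1.10 × baseline makes it computable, but any use at all then fails, and the SAP does not choose between these.

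**The case against.** The strongest reply is that this is a design choice. SAP 9.1.5.1 defines mild, strong and any in sequence, matching the rescue-use endpoints and the two permitted products. Read as any permitted rescue, the rule is explicit and programmable, and prohibited drugs are handled as deviations. That reading fits the rescue-use endpoints. It does not serve the responder condition, because the deviation rule acts only on the per-protocol set and responder rates never use that set.

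The second reply is that the protocol makes such use unlikely. It is prohibited. Inclusion criterion 7 requires willingness to change to permitted rescue from the start of run-in. Sites monitor diaries between visits: "The review of the e-Diary, which covers compliance with e-Diary completion and analgesic use should be performed by site staff regularly". Diaries are reviewed again before randomization, and Protocol 3.6.7 withdraws subjects who require a prohibited treatment. Use would also be visible in the deviation listing and the medication records: "Recording of concomitant medication other than ibuprofen and hydrocodone-acetaminophen will be performed at all visits". All of this lowers the likely frequency, and Case 1, with a full cycle of prohibited use, is an extreme. But withdrawal does not change a cycle already recorded, and listings do not change a responder count.

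The trigger is also narrow. Days with both Other and a rescue product are already counted, at least 3 or 4 Other-only days are needed for a wrong pass on both readings, and the NRS threshold must be met. That stands. So does the point that no statistical test is performed.

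Finally, Protocol 7.2.1.6 defines responders by NRS reduction alone. The analgesic condition appears only in the SAP and is not listed in SAP 12 as a departure from the protocol. This leaves the SAP wording as the only authority for the condition.

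**Conclusion.** The concern holds. Followed exactly, SAP 9.1.5.1 and 9.1.6 treat an Other-only day as analgesic-free at baseline and on treatment, and no other SAP rule corrects this in the ITT responder summary. Subjects can be misclassified in either direction.

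With rescue use unchanged from at least one day, 3 Other-only days in a cycle of 24 to 29 days, or 4 in a cycle of 30 to 35 days, give a wrong pass on either reading of the 10%. These figures assume complete diaries and whole-day counts.

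The number of subjects affected cannot be computed, because the documents do not say how often Other was used; given the prohibition and monitoring it may be small. The consequence is limited to descriptive rates for one secondary endpoint. The primary endpoint, the other endpoints and power are not affected. The unstated scale of the 10% is a separate gap in the same sentence and can affect subjects with no Other use.

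**What to change.** For the responder condition only, define a separately named variable, for example any analgesic including other. Derive it at baseline and in each cycle from all three parts of question 13, or from a yes to question 12, and refer to it in SAP 9.1.6. Leave the mild, strong and any-rescue variables in SAP 9.1.5.1 as they are, so that the rescue-use endpoints do not change.

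In the same edit, state whether the 10% is relative or in percentage points and, if relative, how zero baseline use is handled.

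The cost is two or three lines of SAP text and one derived variable. The data are already collected and no other endpoint changes.
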